7.8 Safety Analyses

The following assessments will be used to evaluate the overall safety of MDNA55:

- Adverse events;
- Vital signs;
- Physical examination;
- · Neurological examinations;
- Electrocardiogram (ECG);
- Clinical laboratory results;
- KPS;
- Antibody Assessment (serum anti-MDNA55 antibody and neutralizing antibody);
- Relationship of safety to evaluation of immune parameters (ADA and NAb).

All safety analysis will be performed using the safety population. All safety endpoints will be summarized according to the following subgroups:

- Overall;
- Grouped by concentration (1.5, 3, 6, and 9 ug/mL);
- Grouped by volumes of infusion (volume of infusion will have two categories);

Medicenna Therapeutics Inc Statistical Analysis Plan Version Final 2.0

Private and Confidential Study Code: MDNA55-05 Date: Oct 23, 2019

7.8.2 Vital Signs

Vital sign measurements will include Pulse (bpm), Respiratory Rate (breaths/min), Weight (kg/lb), Systolic blood pressure (mmHg) and Diastolic blood pressure (mmHg).

Vital signs data will be summarized using descriptive statistics for actual values and changes from baseline. Only subjects with both baseline and post-dose values will be summarized at each schedule visit.

All vital signs data will be provided as a by-subject listing.

7.8.3 Physical examination

Physical examination will be listed for date, visit and examination status (yes/no).

7.8.4 Electrocardiogram (ECG)

Descriptive statistics for the actual values and changes from baseline over time by visit will be summarized for the below ECG parameter:

- QT interval (msec);
- PR interval (msec);
- QRS duration (msec);
- QTc interval (msec);
- Heart rate (bpm).

In case of multiple assessment done on the same date, the latest assessment should be considered for the summarization of the parameters.

ECG overall interpretation and QTc prolongation will be summarized using frequency and percentage for each scheduled visit for safety population.

All ECG values along with the categorical interpretation will be presented in the listings by subject and visit time point.

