7.2.2 Safety Considerations

Physical examinations will be performed at screening, within 24 hours prior to catheter placement and following CED infusion on Days 1 or 2 (according to infusion duration), 14, 30, 60, 90, 120, 180, 240, and 360 (or early termination). The screening and Day 360 (or early termination) examinations will be complete physical examinations; other examinations should be focused, at the discretion of the Investigator, to assess changes from the previous examination. Clinically significant changes in physical examination findings during or after treatment, including transient neurological symptoms, will be reported as AEs.

Other safety assessments will include vital signs. The Investigator or a designated associate will review all vital sign results, and clinically significant findings will be reported as AEs (see Section 8.2.2) and followed or treated according to institutional guidelines or the treating physician's medical judgment. Triplicate twelve-lead ECGs are taken during screening and within 2 hours

following completion of infusion, and clinically significant abnormal findings must be followed by the Investigator.

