- s Vital signs taken after completion of infusion when the subject is ambulatory prior to hospital discharge
- t ECG (triplicate assessment) will be performed at Screening and immediately following completion of infusion (within 2 hours of infusion end time); triplicate assessment in 3 immediate traces

| | otocol # MDNA55-05 ersion: v.6.1 | CONFIDENTIAL |
|---|--|---|
| ı | Blood samples for hematology, serum chemistry, and coagulation (Section 7) | 2.1) shall be taken in parallel with either the PK blood collection |

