6.4 Baseline Definition

The baseline value is defined as the last non missing assessment prior to catheter placement.

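### Triplicate ECGs are collected, but the SAP summarises only the latest same-date trace and has no rule for averaging the three

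*SAP*

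**What the plan says.** Protocol 7.2.2 sets the collection: "Triplicate twelve-lead ECGs are taken during screening and within 2 hours" of the end of infusion. Footnote t to Protocol Table 7 adds how this is done: "triplicate assessment in 3 immediate traces". The SAP carries the same footnote under its own Table 2. Both schedules show ECGs at these two time points only.

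SAP 7.8.4 then gives the summary rule for several ECGs taken on one date: "the latest assessment should be considered for the summarization of the parameters". SAP 6.4 sets baseline for all variables: "The baseline value is defined as the last non missing assessment prior to catheter placement". Neither document mentions a mean or median of the three traces.

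SAP 7.8.4 plans two kinds of summary. One is continuous, for QT, PR, QRS, QTc and heart rate: "Descriptive statistics for the actual values and changes from baseline over time by visit will be summarized for the below ECG parameter". The other is categorical: "ECG overall interpretation and QTc prolongation will be summarized using frequency and percentage for each scheduled visit for safety population". It states no prolongation cut-off and does not say which of the three traces decides the category. The individual readings are kept: "All ECG values along with the categorical interpretation will be presented in the listings by subject and visit time point".

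**The concern.** A triplicate is useful because averaging three readings taken moments apart reduces beat-to-beat and reading noise. Three immediate traces will normally share a date, so the same-date rule applies to them. With only two scheduled ECG time points, the triplicate is also the only scheduled source of several ECGs on one date. The rule therefore falls mainly on the triplicates, and the baseline definition does the same at the other end of the change score.

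What is at stake is precision in a descriptive safety table. There is one post-infusion ECG time point and about 52 subjects, so no later scheduled ECG would smooth a noisy reading.

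**Working it through.** **Inputs from the documents.** Three traces per time point; two time points; latest same-date value used; last non-missing value as baseline; about 52 subjects. The documents state no ECG variance, QTc cut-off or ECG precision target, so there is no planned figure to reproduce.

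**Share of readings left out of the summaries.** 1 − 1/3 = 2/3 at each time point.

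**Noise model (assumed).** Let s_w be the SD between traces within a triplet, and s_b the SD between occasions in the same subject, which the three traces share. With no true between-subject variation in change:

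- latest trace at both ends: SD of change = √[2(s_b² + s_w²)]
- triplicate mean at both ends: SD of change = √[2(s_b² + s_w²/3)]

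The assumed ranges are s_w 5-10 ms and s_b 5-8 ms. At the four corners:

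| s_w | s_b | Latest trace | Triplicate mean | Variance removed |
|---|---|---|---|---|
| 5 | 5 | √[2(25+25)] = 10.0 ms | √[2(25+8.33)] = 8.2 ms | 16.67/50 = 33% |
| 5 | 8 | √[2(64+25)] = 13.3 ms | √[2(64+8.33)] = 12.0 ms | 16.67/89 = 19% |
| 10 | 5 | √[2(25+100)] = 15.8 ms | √[2(25+33.33)] = 10.8 ms | 66.67/125 = 53% |
| 10 | 8 | √[2(64+100)] = 18.1 ms | √[2(64+33.33)] = 14.0 ms | 66.67/164 = 41% |

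**Bounds on the ratio.** If the three traces shared no error, a single trace would have 3 times the noise variance of the mean, or √3 = 1.73 times the SD. If 25%, 50% or 75% of the within-time-point variance is shared, the SD ratio falls to 1.41, 1.22 or 1.10.

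**Why this is an upper range on these SDs.** Averaging removes 2 × (2/3)s_w² = (4/3)s_w² from the variance of the change, and nothing else. If subjects truly differ in their QTc change, with variance τ², the proportional saving is (4/3)s_w² / [2(s_b² + s_w²) + τ²]. This shrinks as τ² grows.

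**Illustration for prolongation counts.** The plan gives no cut-off. Take an increase above 30 ms as an assumed one, with no true change and normal errors. The chance of a false flag per subject is:

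- s_w = s_b = 5: 30/10.0 = 3.00 SDs, 0.1%, with the latest trace; 30/8.2 = 3.7 SDs, 0.01%, with the mean
- s_w = 10, s_b = 8: 30/18.1 = 1.66 SDs, 4.9%, with the latest trace; 30/14.0 = 2.15 SDs, 1.6%, with the mean

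At the noisier end that is 52 × 0.049 = 2.5 subjects against 52 × 0.016 = 0.8.

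**The case against.** The strongest reply concerns wording. The schedule footnotes call the set of three traces one triplicate assessment, so the latest assessment could mean the later of two triplicate sessions on one day. That reading is possible. It does not rescue the text, because the SAP would then have no rule for turning three readings into one value, and a programmer could not produce the table without inventing one. The same correction is needed.

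A reader might also infer several stronger things that the documents do not support:

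- **That two thirds of the ECG data are discarded.** The rule governs the summaries. All values go into the listings, so triplicate means can still be computed.
- **That a confidence interval for QTc change is widened.** SAP 7.8.4 plans descriptive statistics, which SAP 7.1 defines without an interval. The protocol's general intention to give intervals where appropriate does not name ECG.
- **That the prolongation table is shown to contain false outliers.** No cut-off is stated, prolongation could be a recorded category, and the latest-assessment sentence is not expressly applied to that count. Its use there is only implied.
- **That the mean change is biased.** Taking the last of three immediate traces adds variance and does not by itself shift the mean.
- **That QTc change is the principal ECG result.** It is one of five listed parameters, and both documents say that systemic exposure is not expected.

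It also stands that every SD used here is assumed. Real variation in change is likely to matter: baseline may be up to 14 days before treatment, and the second ECG follows surgery, anesthesia and a 24-48 hour infusion.

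**Conclusion.** The point holds as a minor, nearly free improvement. On the natural reading, one trace of three feeds each end of the ECG change score. On the alternative reading, the rule for combining the traces is missing. Under the assumed SDs and no true between-subject variation in change, the SD of QTc change is 10.0-18.1 ms with single traces and 8.2-14.0 ms with triplicate means, a variance reduction of 19-53%. Any true variation in change makes the gain smaller. The loss is one of precision in descriptive safety summaries. No efficacy result depends on it, and the survival analysis is unaffected.

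**What to change.** Two SAP edits are needed, because changing 7.8.4 alone would leave it in conflict with 6.4.

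- **SAP 7.8.4:** state that the mean of the triplicate readings is the value for each ECG parameter at each time point and is used for the QTc prolongation categories. Limit the latest-assessment rule to repeat sessions on the same date.
- **SAP 6.4:** add that the ECG baseline is the mean of the last triplicate before catheter placement.

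While 7.8.4 is open, it should also name the QTc correction and the prolongation categories, which it now leaves undefined. The overall interpretation is categorical and cannot be averaged, so if it is recorded per trace the SAP should say which reading is tabulated.

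The cost is a few sentences and a small programming change. No new data are needed, since all three traces are already collected and listed.

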7.8.5 Clinical Laboratory Results

Laboratory parameters include:

- Hematology: hemoglobin, hematocrit, platelet count, white blood cell (WBC) count, and WBC differential.
- Coagulation: prothrombin time (PT)/PTT/INR (PTT, corrected, if necessary);

- Serum chemistry: AST, ALT, lactate dehydrogenase (LDH), total bilirubin, indirect bilirubin, alkaline phosphatase, total protein, albumin, sodium, potassium, chloride, carbon dioxide, calcium, phosphorus, blood urea nitrogen (BUN), creatinine, uric acid, and glucose
- Urinalysis: pH, specific gravity, protein, glucose, ketones, blood, leukocyte esterase, and nitrite. Microscopy required only to follow-up clinically significant abnormal findings
- Pregnancy: Serum pregnancy tests will be performed at screening and at 30 and 180 days post CED infusion for all women of childbearing potential

Descriptive statistics for the actual values (and/or change from baseline) for the selected hematology, chemistry, coagulation and urinalysis laboratory parameters will be summarized at each scheduled visit. Parameters with categorical values will be summarized by count and percentages.

Listing of all laboratory data with values flagged to indicate the corresponding classifications relative to the laboratory normal ranges (Low, Normal, High).

Coagulation (prothrombin time [PT], partial thromboplastin time [PTT]), international normalized ratio [INR]), urinalysis, and pregnancy test results will also be listed.

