7.2.1 Laboratory Evaluations

All study sites will conduct their own hematology, serum chemistry, and urinalysis tests (within their respective local certified laboratories) at various time points for each subject (see Table 7).

Required clinical laboratory tests for each panel will be as follows:

 Hematology: hemoglobin, hematocrit, platelet count, white blood cell (WBC) count, and WBC differential;

- Coagulation: prothrombin time (PT)/PTT/INR (PTT, corrected, if necessary);
- Serum chemistry: AST, ALT, lactate dehydrogenase (LDH), total bilirubin, indirect bilirubin, alkaline phosphatase, total protein, albumin, sodium, potassium, chloride, carbon dioxide, calcium, phosphorus, blood urea nitrogen (BUN), creatinine, uric acid, and glucose;
- Urinalysis: pH, specific gravity, protein, glucose, ketones, blood, leukocyte esterase, and nitrite. Microscopy required only to follow-up clinically significant abnormal findings; and
- Pregnancy: Serum pregnancy tests will be performed at screening and at 30 and 180 days post CED infusion for all women of childbearing potential.

The Investigator or a designated associate will review all clinical laboratory results, and clinically significant findings will be reported as AEs (see Section 8.2.2) and followed or treated according to institutional guidelines or the treating physician's medical judgment.

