8.2 Evaluation of Safety

Each subject receiving MDNA55 via CED will be evaluable for safety. Safety parameters include all laboratory tests and hematological abnormalities, physical findings, ECG, imaging parameters and AEs.

Each subject will be assessed periodically for the development of any toxicity as outlined in Section 7.5.

Definitions and reporting procedures for AEs provided in this protocol comply with current ICH E6 and other applicable international and local regulatory requirements. The Medical Monitor will promptly review all information relevant to the safety of MDNA55. The Investigator will carefully monitor each subject throughout the study for AEs and all AEs will be followed until adequately resolved. CTCAE 4.0 will be used to determine severity of AEs and SAEs.

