9.2.6 Analysis of Safety Variables

Safety variables, including AEs, laboratory results, vital signs, ECGs, antibody assessments, and serum drug levels on PK samples, will be summarized and presented, by study time where appropriate.

AEs will be coded using the Medical Dictionary for Regulatory Activities (MedDRA). Cancer Therapy Evaluation Program (CTEP) Common Terminology Criteria for Adverse Events NCI CTCAE v4.0 will be used to grade the severity of AEs. Treatment emergent AEs will be summarized by system organ class (SOC) and by preferred terms for all treated subjects and subset of subjects of interest. Certain summaries of the treatment-emergent AEs will also be generated by severity, relationship to study drug, relationship to infusion, catheter placement, volume of infusate, and prior therapies. Proportion of patients experiencing Grade 3 and 4 laboratory test results will be summarized.

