7. STATISTICAL METHODOLOGIES AND ANALYSES

7.1 General Statistical Conventions

All statistical analysis will be performed using SAS® version 9.3 or above. Summary tables (descriptive statistics and/or frequency tables) will be provided for baseline variables, efficacy variables and safety variables. Continuous variables will be described by descriptive statistics (n, mean, standard deviation, minimum, maximum, median. Frequency counts and percentage of subjects within each category will be provided for categorical data. Summaries will be provided for overall treatment.

Decimal Precision Convention: Means and medians will be reported to one decimal place more than the raw data. Standard deviation will be reported to two more decimal places than the raw value. The minimum and maximum will be reported to the same decimal as the raw data. In case of n<2, where n indicates the number of evaluable subjects at the particular time point, only n, mean, minimum and maximum will be displayed. The statistic "Missing" will also be evaluated by enumerating the number of missing entries/subjects, if any at that visit, and presented as a summary statistic only for the resulting time points.

Categorical variables will be summarized using the frequency count and the percentage of subjects in each category. All percentages will be rounded to one decimal point. The number and percentage of subjects will always be presented in the form XX (XX.X). To ensure completeness, all summaries for categorical and discrete variables will include all categories, even if none of the subjects are in that category. Counts of zero in any category will be presented as "0". Unless otherwise noted, for all percentages, the number of subjects in the analysis population for the treatment group will be the denominator.

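### The protocol promises the proportion of patients with Grade 3 and 4 laboratory results, but SAP 7.8.5 derives no grade and plans no table that gives it

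*SAP*

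**What the plan says.** **Protocol.** Section 9.2.6 (Analysis of Safety Variables) lists, after the adverse-event summaries, a separate laboratory result: "Proportion of patients experiencing Grade 3 and 4 laboratory test results will be summarized". The only grading scale the protocol names is the NCI CTCAE, and it names it for adverse events: "CTCAE 4.0 will be used to determine severity of AEs and SAEs" (8.2; also 8.2.2.2 and 9.2.6). Section 7.2.1 sets out how a laboratory value can become an adverse event: "The Investigator or a designated associate will review all clinical laboratory results, and clinically significant findings will be reported as AEs". Section 8.2.2 defines clinically significant abnormalities as those the Investigator so identifies, those needing intervention, or both.

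**SAP.** Section 7.8.5 (Clinical Laboratory Results) plans three kinds of output:

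- Summaries by planned visit: "Descriptive statistics for the actual values (and/or change from baseline) for the selected hematology, chemistry, coagulation and urinalysis laboratory parameters will be summarized". SAP 7.1 gives the content: "Continuous variables will be described by descriptive statistics (n, mean, standard deviation, minimum, maximum, median".
- Frequencies for categorical parameters only: "Parameters with categorical values will be summarized by count and percentages".
- Data listings, of which the main one is a "Listing of all laboratory data with values flagged to indicate the corresponding classifications relative to the laboratory normal ranges (Low, Normal, High"), with further listings for coagulation, urinalysis and pregnancy tests.

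The SAP introduction says the plan implements Protocol Version 6.1, the version in hand. SAP section 9, reserved for changes from the protocol, shows a heading and no text.

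**The concern.** A result that the protocol commits to has no method in the SAP section where it belongs, and no change is declared. A team that programs 7.8.5 as written will produce laboratory tables from which the promised proportion cannot be read.

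What is at stake is the laboratory safety summary of a single-arm trial of about 52 subjects. In a trial of that size, severe laboratory abnormalities would be a handful of subjects, so the useful summary is a count of subjects at each severe grade. By-visit distributions do not give that count. A Low or High flag is the same for a value just outside the normal range and for one far outside it.

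**Working it through.** The documents give no figure to reproduce, so the check is mainly a comparison of texts. A small illustration shows what each planned output can and cannot tell the reader.

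**Step 1. What the promised result needs.** It needs a grade for each laboratory value, a worst grade per subject, and the number of subjects at Grade 3 and Grade 4 over the number treated.

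**Step 2. Can each output in SAP 7.8.5 supply it?**

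| Output in SAP 7.8.5 | What it shows | Number of subjects at Grade 3 or 4? |
|---|---|---|
| n, mean, SD, median by scheduled visit, selected parameters | Centre and spread | No |
| Minimum and maximum by scheduled visit, selected parameters | The most extreme value at that visit | No: one value, not a count of subjects |
| Counts and percentages | Parameters whose values are categorical | No: no grade is derived to serve as a category |
| Listing with Low/Normal/High flag | Every numeric value with its flag | Only by hand: no grade is attached and nothing is tabulated |

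**Step 3. Unscheduled results.** The summaries are tied to scheduled visits, and SAP 6.3 says visit windowing does not apply. Protocol 7.5.3.2 allows further assessments at the Investigator's discretion to follow up adverse events. A severe value found that way has no stated route into a table and appears only in the listing.

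**Step 4. Is the result planned elsewhere in the SAP?** In the available text, the word grade occurs only for tumour grade among the baseline characteristics (7.4.2). The numbering goes from the opening of 7.8 to 7.8.2, so 7.8.1 cannot be read. The table templates are in a separate document.

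**Step 5. Illustration.** The values and counts are assumed; only the 52 and 46 come from the documents.

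- One subject rises from 30 to 600 U/L at one visit. The mean of 52 moves by (600 − 30)/52 = 11.0 U/L, and the maximum reads 600.
- Three subjects make the same rise. The mean moves by 3 × 570/52 = 32.9 U/L, and the maximum still reads 600. The maximum does not separate one subject from three.
- The missing table would separate them. With exact Clopper-Pearson 95% intervals: 3/52 = 5.8% (1.2% to 15.9%); 3/46 = 6.5% (1.4% to 17.9%); 0/52 = 0% (0 to 6.8%); 0/46 = 0% (0 to 7.7%).

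**The case against.** The strongest reply has four parts.

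**Extreme values are not hidden.** A reader might infer from the flags that 7.8.5 gives only means and that a severe value would go unseen. The documents do not support that. SAP 7.1 includes minimum and maximum, change from baseline may be shown, and the listing prints the number beside the flag. This part stands. The gap is the count and proportion of subjects, and the tabulation of unscheduled or unselected results.

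**The adverse-event route exists.** Clinically significant findings become adverse events, are graded by CTCAE v4.0, and are summarised by severity under Protocol 9.2.6. So severe laboratory toxicity is not left wholly unseparated. But that route covers only values judged significant or needing intervention, and the protocol lists the laboratory proportion in addition to the adverse-event summaries. It does not replace the promised result.

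**Part of the SAP cannot be read.** Section 7.8.1, by position probably adverse events, and the table templates might hold a graded laboratory table. That cannot be excluded, and absent text is not an error in the plan. It limits the claim to 7.8.5, which appears complete and is where the method should be. For the same reason it would be too strong to say that the SAP has replaced or withdrawn the protocol's analysis. No available text does so.

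**There is no sign of a laboratory toxicity problem.** A reader might add urgency because the drug carries a potent toxin. The documents do not support that either. Protocol 7.2.3 and SAP 7.9 say systemic exposure is not expected and that circulating drug was not detected in previous clinical studies. The point rests on the mismatch between the two documents alone.

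**Conclusion.** The point holds in a limited form. Protocol 9.2.6 commits to a Grade 3 and 4 laboratory proportion. SAP 7.8.5 neither derives a grade nor plans a table giving the number or proportion of subjects who reach one, and SAP section 9 declares no change in the available text. The size is one missing safety summary; no efficacy result, sample size or error rate is affected. It is a worthwhile, low-cost correction and not a threat to the trial's conclusions.

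The conclusion rests on three assumptions: that 7.8.5 is complete as it appears; that 7.8.1 and the templates do not already contain the table; and that CTCAE v4.0 is the intended scale for laboratory grades. The last is the natural reading because the protocol names no other scale, but the protocol states it only for adverse events.

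**What to change.** In SAP 7.8.5, derive the CTCAE v4.0 grade for every gradable laboratory parameter and say that this is the scale used. For the Safety population, tabulate by parameter the number and percentage of subjects whose worst post-baseline grade is 3 and whose worst is 4, using scheduled and unscheduled results. If the table is already in 7.8.1 or the templates, a cross-reference in 7.8.5 is enough. If the sponsor means to drop it, record and justify that in SAP section 9.

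A shift table from baseline grade to worst grade and exact confidence intervals would be useful, but they go beyond the protocol's promise and are optional.

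The table uses laboratory results the protocol already collects. The cost is modest programming plus harmonisation of ranges and units, because each of up to 12 sites uses its own local laboratory (Protocol 7.2.1). The change affects reporting only and touches no dose or clinical rule.
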